5.4 Risks and anticipated adverse device effects that are to be assessed

The investigational device is a marketed, CE-certified product, which will be used within its intendent purpose. Rate of defect treatment complications (during index defect treatment and in follow-up treatments) and rate of SAEs related to defect treatment will be assessed. The term "defect treatment related" represents not only device-related but in total procedure-related AEs of special interest and SAEs. Non-serious AEs which are not classified as "of special interest" will not be assessed.

6. Design of the clinical study

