6.3.6 Expected duration of each subject's participation

The mean follow-up period (from date of enrolment to end of follow-up) of all patients is expected to be about 3 months.

6.3.7 Number of subjects required to be included in the study

As discussed in 3.2, the evidence for the different treatment options is very limited. Especially the patient populations, e.g. regarding underlying diseases, as well as the processes in the therapy are very different in the individual studies published. Therefore a reasonable sample size calculation is not possible at the moment. Thus, an interim analysis with sample size re-calculation is planned.

The best evidence for an **initial sample size calculation** is provided by data of the study by Wasmann et al. [29], a cohort study including 334 patients with ileal defects, where EVAC therapy was compared to conventional management of defect treatment. The median time to stoma relocation was estimated as 4 months in the EVAC group (interquartile range 3 to 6 months) versus 4 months (3 to 13 months) in the conventional management group. Therefore, the proportion of patients with stoma relocation after 6 months is known as 75% in the EVAC group. Assuming a constant increasing proportion in the conventional management group from 4 to 13 months with 2.8% per month, a proportion of 56% stoma relocations after 6 months is expected for the conventional group. Even if the follow-up is set to 3 months in this study, sample size calculation can be based on 6 months results.

Sample size calculation was performed with PASS 16.0.3 using a two-sided, one-sample log rank test. A group sequential design with the alpha spending function of O'Brien-Fleming results in a two-sided type one error of 4.92% for the final analysis. A sample size of 99 analysable subjects achieves 80% power to detect shorter time to release for food intake or endoscopic release for stoma relocation (assuming a proportion of relocated stoma of 75% after 6 months in the EVAC group when the proportion in the historic control group is 56%). The expected number of events during the study with 3 months of follow-up is 13. It is assumed that the survival time distributions of both groups are approximated reasonable well by the Weibull distribution with a shape parameter of 1.00. To account for treatment switching and early drop-outs of 10%, 110 analysable patients will be enrolled.

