6.4 Procedures

6.4.1 Study-related procedures

No study-specific procedures are defined in this protocol and will be performed during this observational study but routine clinical care procedures according to applicable medical guidelines, IFU of the devices used and local policy.

"**Enrolment**" in this observational study means the patient is giving informed consent for use of personal medical data, i.e. the legal prerequisite for being part of this clinical observation. Thus, "**date of enrolment**" is the date of the signature on informed consent. In this purely observational study consent for use of data might be given after index treatment because this treatment is performed in routine clinical care without any studyspecific requirements or definitions and might be performed in an acute setting.

"**Baseline visit**" in this observational study is not a specific personal visit of the patient at the study site but a basket to document all relevant data known at baseline. Thus, medical data reported at baseline visit might represent patient's status even before enrolment, e.g. data on medical history. Use of these data is covered by the informed consent given by the patient.

Due to the acute defects in focus and the corresponding indication of invasive treatment in this purely observational study, "date of enrolment" (=date of informed consent for use of personal medical data) might therefore be after "date of index treatment".

"Start of observation" with respect to the objectives and endpoints of this study is the time point of the index treatment.

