6.4.5 Follow-up (FU) visits

Every patient will be followed for 3 months after discharge after index treatment.

In line with routine clinical care, at least one personal follow up visit should take place within 3 months of follow up. To ensure comparability of data, in case this follow up visit has not been performed after 3 months (± 2 weeks) in addition a phone call with the patient should provide final information to be documented in the FU visit (phone) of the e-CRF.

At the FU visits the following data from clinical routine will be documented in the e-CRF (if available):

- Patient status
- Relevant concomitant medication and other treatment
- Safety related events: SAEs (including SADEs), AEs of special interest (including ADEs) and DD

Assessments*	Baseline visit	Index-Treatment	FU visits
Informed consent for data use	Х		
In- and Exclusion criteria	Х		
Demographic data	Х		
Medical history	Х		
Patient's status	Х		X**
Medication/other treatment	Х	X	X**
Concomitant diseases	Х		
Data regarding index treatment and related therapy		X	
Outcome of index treatment		X	
Safety related events (SAEs, SADEs, ADEs, DD)		X	Х

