Patients undergoing the procedures of interest in this study will often be in a clinical situation requiring immediate therapy without any delay. In addition, it is expected that potential study patients might not be able to give informed consent on the use of their personal data at the time of physician's decision on the primary intervention procedure of interest. Since this clinical study is purely observational, all therapies used are decided individually by the treating physician in routine clinical care in line with medical guidelines and the IFUs of the devices used but not pre-defined in the study protocol. Thus, informed consent for use of personal data will be given subsequent to the primary intervention procedure of interest but before any data transfer to the e-CRF.

Should there be any modifications to the protocol, such that this would directly affect the patient's consent for transfer, processing and use of their personal medical data in the study, an addendum to the informed consent form specifying the modification must be compiled and the active patients must agree to sign this addendum indicating that they also agree to the modifications within the study.

A signed copy of the patient's informed consent form must be maintained in the study file on site, a copy of the signed informed consent form must be provided to the study patient. The patient's permanent medical records should indicate the patient's study participation.

14. Adverse events, adverse device effects and device deficiencies

SAEs will be documented following ISO 14155:2020 and reported in accordance with applicable national standards. Since the study is observational, all therapies and procedures represent routine clinical care in line with applicable medical guidelines, market authorisations and corresponding IFUs. Since no risks or benefits compared to routine clinical care will be added, the rate of non-serious AEs will be identical to routine clinical care. Thus, non-serious AEs will not be documented within this study but AEs of special interest (AEoSI), only (refer to section 14.1).

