14.1 Definitions

Adverse Event (AE):

Is any untoward medical occurrence, unintended disease or injury, or untoward clinical signs (including abnormal laboratory findings) in subjects, users or other persons, in the context of a clinical investigation, whether or not related to the investigational medical device. This definition includes events that are anticipated as well as unanticipated events and those occurring in the context of a clinical investigation related to the investigational device, the comparator or the procedures involved. For users or other persons, this definition is restricted to events related to investigational medical devices. A newly diagnosed concomitant disease is also considered an AE.

AE of special interest (AEoSI)

Potential complication of index therapy:

- latrogenic injury of the mucosa;
- Any bleeding, appearance of fistula or abscess, pneumonia, peritonitis, or mediastinitis as a symptom of the treatment;
- Occurrence of stricture / stenosis during the follow-up.

An independent CEC will review AEoSIs based on coded (pseudonymized) copies of corresponding medical files to assess if they fulfil criteria for

Serious Adverse Event (SAE):

A **SAE** is any untoward medical occurrence that

- led to death,
- Ied to serious deterioration in the health of the subject, that either resulted in
 - > a life-threatening illness or injury, or
 - > a permanent impairment of a body structure or a body function, or
 - > hospitalisation or prolongation of patient hospitalisation, or
 - medical or surgical intervention to prevent life-threatening illness or injury or permanent impairment to a body structure or a body function,
 - > a chronic disease,
- Ied to foetal distress, foetal death or a congenital abnormality or birth defect.

More than one of the above criteria can be applicable to each event.

These characteristics/consequences have to be considered at the time of the event. For example, regarding a life-threatening event, this refers to an event in which the subject was at risk of death at the time of the event. It does not refer to an event which hypothetically might have caused death if it were more severe.

NOTE:

- The index treatment itself,
- a planned hospital overnight stay in follow-up for review of index defect,
- an elective hospitalisation (e.g. surgery) verifiably planned before signing consent
- overnight survey visits (e.g. sleep lab)

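### The time limit on stricture/stenosis in section 14.1 leaves a small gap against section 5.4: a non-serious stricture before follow-up starts need not be an AE of special interest

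*Protocol*

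**What the plan says.** The AEoSI list in section 14.1 has three entries. Mucosal injury, and the group of bleeding, fistula, abscess, pneumonia, peritonitis and mediastinitis, carry no time window. The third reads "Occurrence of stricture / stenosis during the follow-up".

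Whether an event is on this list decides whether it is captured when it is not serious. Section 5.4: "Non-serious AEs which are not classified as 'of special interest' will not be assessed". The opening of section 14 repeats the rule for documentation. Under 1.2 and 14.1 the CEC reviews SAEs and AEoSIs.

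The intended scope is wider. Section 5.4: "Rate of defect treatment complications (during index defect treatment and in follow-up treatments) and rate of SAEs related to defect treatment will be assessed". For the start of observation, 6.4.1 says that it "with respect to the objectives and endpoints of this study is the time point of the index treatment". Section 14.3 collects SAEs from the start of index treatment.

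Follow-up has two stated starting points. Section 6.4.5: "Every patient will be followed for 3 months after discharge after index treatment". Section 6.3.6: "The mean follow-up period (from date of enrolment to end of follow-up) of all patients is expected to be about 3 months".

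**The concern.** One complication is given a later start than the rate it belongs to. Under either stated starting point, some time after index use lies outside the stricture window but inside the period that 5.4 says will be assessed. A non-serious stricture found in that time does not meet the AEoSI definition, so nothing requires it to be entered as one or adjudicated.

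Confirming safety is among the study objectives (5.2), and stricture is one of the complications on which the background in 3.2 contrasts endoscopic vacuum therapy (EVT) with stents (9.4% against 28.2%). A window whose start differs from patient to patient makes the study's own stricture rate harder to interpret.

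**Working it through.** The protocol states no planned stricture or complication rate, so there is no figure to reproduce. The check is mainly textual.

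**Step 1: what the window leaves out, by reading of follow-up.**

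| Follow-up starts at | Source | Time outside the stricture window |
|---|---|---|
| Discharge | 6.4.5 | Index use to discharge |
| Enrolment (consent date) | 6.3.6 | Index use to signature; 6.3.4 expects most patients to consent after treatment of the index defect |
| After the first device use | Inferred from 6.1.3, which defines index therapy as the first use | Little |

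The first two are stated and both leave a gap. The third is possible but nowhere given as a definition.

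**Step 2: what is captured in that time by other routes.**

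- SAE: all SAEs from start of index treatment (14.3), including events that prolong hospitalisation (14.1). An SAE form is requested where seriousness is in doubt.
- Device-related events: recorded under 14.2 without a seriousness or time limit. ADEs are ticked for the index-treatment visit in the visit table.
- EVT-specific findings at the index-treatment visit (6.4.4): an open list that does not name stricture.

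What remains is a stricture that is non-serious, not judged device-related and found before follow-up starts. It might be noted among the EVT-specific findings, but nothing routes it from there to the CEC.

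**Step 3: visit table.** Section 6.4.5 lists AEs of special interest among the safety data. The safety row of the visit table names SAEs, SADEs, ADEs and DD, and omits them.

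**Step 4: illustration of size.** Two EVT series in 3.2 give 4/52 = 7.7% (prospective cohort) and 3/32 = 9.4% (retrospective comparison with stents; its stent arm, 11/39 = 28.2%, also reproduces). With 110 patients, the expected strictures are 110 × 4/52 = 8.5 and 110 × 3/32 = 10.3. Let *s* be the share that falls in the residual gap. The protocol does not give *s*, so the values below are assumptions. Missed = 110 × rate × *s*; recorded rate = rate × (1 − *s*).

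| *s* | Missed strictures | Recorded rate, from 7.7% | Recorded rate, from 9.4% |
|---|---|---|---|
| 0% | 0 | 7.7% | 9.4% |
| 10% | 0.8 to 1.0 | 6.9% | 8.4% |
| 25% | 2.1 to 2.6 | 5.8% | 7.0% |
| 50% | 4.2 to 5.2 | 3.8% | 4.7% |

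Pooling the six series in 3.2 that give a stricture or stenosis count gives (0+2+3+2+4+1)/(10+5+32+14+52+5) = 12/118 = 10.2%. Of those 118 patients, 113 had upper GI defects, while 6.3 plans roughly equal numbers of upper and lower GI treatments. These rates set a scale; they do not predict this study's rate.

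**The case against.** A reader might infer that strictures seen during the index stay are simply not recorded. The protocol does not support that. The routes in step 2 capture serious and device-related strictures, and 6.4.3 has data on the entire stay documented. Under the enrolment-based definition, part of the stay may itself count as follow-up.

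A reader might also infer that the complication rate is shown to be understated, or that it could not be set beside published rates. That is not supported either. Where the series in 3.2 give timing, stricture was seen after completion of EVT or during follow-up, which suggests that few may fall in the gap. No stricture comparison is planned. Nor does the share of patient time before discharge measure missed events, since that would need a constant risk over time, which the cited timing does not suggest.

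Finally, the secondary safety endpoint counts related SAEs only, so a non-serious stricture never enters it.

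All of this limits the size of the point and stands. It does not remove the inconsistency. After EVT is not the same as after discharge, and the stent comparison gives no timing for its three strictures. The device-related route needs attribution to the device, whereas 5.4 counts procedure-related events too, and 14.3 says that causal relationships to an investigational device or procedure will not be assumed.

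**Conclusion.** The point holds as a minor inconsistency of definition. As written, 14.1 lets a non-serious stricture that is not judged device-related, and is found between index use and the start of follow-up, escape AEoSI recording and CEC review, although 5.4 includes index defect treatment in the complication rate. The direction is certain, because a narrower window can only lower the count. The size is unknown: in the illustration it runs from none to about five patients in 110, the upper end resting on an assumed 50% share. The conclusion takes follow-up to start where 6.4.5 or 6.3.6 puts it; if it started right after the first device use, the gap would nearly vanish. No primary or secondary endpoint is affected.

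**What to change.** 1. In 14.1, replace the time limit on stricture/stenosis with *at any time from start of index treatment to end of observation*. The start then matches the SAE window in 14.3, and the scope matches 5.4.
2. Define the start of follow-up once, and reconcile 6.3.6 and 6.4.5 with it.
3. Add AEs of special interest to the safety row of the visit table, for both the index-treatment and FU columns, as 6.4.5 already lists them.

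The cost is protocol and e-CRF wording. The data come from routine files and no procedure is added. The CEC may have a few more events to review, and the reported stricture rate may be slightly less favourable.

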14.2 Device Related Adverse Events

Within this PMCF study adverse events related to the IP will be recorded and reported.

14.2.1 Device Deficiency (DD)

DD means any inadequacy in the identity, quality, durability, reliability, safety or performance of an investigational device, including malfunction, use errors or inadequacy in information supplied by the manufacturer. Since the study is observational, no investigational medical product will be used but all therapies and procedures represent routine clinical care in line with applicable medical guidelines, market authorisations and corresponding IFUs. Treating physicians have to report DDs related to medical devices or therapies to the corresponding manufacturers of devices concerned. Reporting duties of manufacturers of devices used within this observational study have to follow routine procedures relevant for marketed medical devices.

14.2.2 Adverse Device Effect (ADE)

Any untoward and unintended response to a medical device. This definition includes AEs resulting from insufficient or inadequate instructions for use, deployment, implantation, installation, or operation, or any malfunction of the investigational medical device. It also includes any event resulting from use error or from intentional misuse of the investigational medical device. Since the study is observational, no investigational medical product will be used but all therapies and procedures represent routine clinical care in line with applicable medical guidelines, market authorisations and corresponding IFUs. Treating physicians have to report ADEs related to medical devices or therapies to the corresponding manufacturers of devices concerned. Reporting duties of manufacturers of devices used within this observational study have to follow routine procedures relevant for marketed medical devices.

14.2.3 Serious Adverse Device Effect (SADE)

Any device deficiency that might have led to a SAE if appropriate action had not been taken, intervention had not occurred, or circumstances had been less fortunate, shall be documented throughout a clinical investigation and appropriately managed by the sponsor. Since the study is observational, no investigational medical product will be used but all therapies and procedures represent routine clinical care in line with applicable medical guidelines, market authorisations and corresponding IFUs. Treating physicians have to report ADEs related to medical devices or therapies to the corresponding manufacturers of devices concerned. Reporting duties of manufacturers of devices used within this observational study have to follow routine procedures relevant for marketed medical devices.

14.3 Recording and reporting of reportable events

The following events are considered reportable events in accordance with MDR Art. 80(2):

- any SAE that has a causal relationship with the investigational device, the comparator or the investigation
 procedure or where such causal relationship is reasonably possible;
- any DD that might have led to a SAE if appropriate action had not been taken, intervention had not occurred, or circumstances had been less fortunate;
- any new findings in relation to any event referred to in the points above.

Since this study is observational, no investigational medical product will be used but all therapies and procedures represent routine clinical care in line with applicable medical guidelines, market authorisations and corresponding IFUs. Thus, causal relationships of events to an investigational device or procedure will not be assumed. However, irrespective of this study, treating physicians have to report AEs related to medical devices or therapies to the corresponding manufacturers of devices concerned. Reporting duties of manufacturers of devices used within this observational study have to follow routine procedures relevant for marketed medical devices.

Information on all SAEs which occurred after start of index treatment, whether related or not related to index treatment, must be collected. The investigator should specify and report in the e-CRF the nature of the sign or symptom leading to the SAE, the date of onset of the sign or symptom, the date of resolution of the specific event (not of the underlying disease), the intensity, interventions performed (if any), the relationship to index treatment, and the outcome.

All SAEs must be reported expeditiously by the investigator to the sponsor through the SAE section of the e-CRF within 24 hours of becoming aware of the event. A SAE form within the e-CRF should be completed for any event where doubt exists regarding its status of seriousness. As a minimum, the investigator has to fill out the following items in the internet-based SAE form within 24 hours of becoming aware of the event:

- Type of event
- Description
- Date of onset
- Criteria for seriousness

As soon as further information regarding the event is available, the investigator should complete the documentation in the e-CRF and sign it electronically. Copies of relevant medical documents, of reports regarding examinations carried out and/or diagnostic findings should be digitally provided to the CRO after adequate blinding of patient identifiers, only.

Follow-up of any **SAE that is fatal or life threatening** should be digitally provided immediately but no later than within **2 calendar days of becoming aware of the event.**

Any SAE reporting (initial reporting and follow-up information on e.g. changes of an ongoing SAE's intensity or relationship to the investigational product or outcome) is done through the SAE section of the e-CRF. An automated e-mail notification system within the e-trial management system will inform the CRO instantaneously, thus, no extra SAE form needs to be transmitted but the CRO will receive an automated digital notification on the SAE at the same time of the data being documented or changes of relevant SAE data being made in the e-CRF.

The investigator shall report in detail all SAEs as well as AEoSIs.

